## 6.5.2 Pharmacodynamics Evaluations

Pharmacodynamic analyses will be conducted on data from participants in the PD Analysis Set. Descriptive statistics will be presented for plasma kallikrein activity levels (as measured by %cHMWK), absolute change and percentage change from baseline levels will be analyzed at each visit. A test comparing the percent change and absolute change from baseline within each group will be calculated and a within group p-value will be presented at each visit and timepoint.

Mean and median activity levels versus time, change from baseline, and percent change from baseline profiles will be plotted by treatment on a linear scale. Individual levels versus time plots by cohort and spaghetti plots with subject level versus time profiles by cohort will also be provided on a linear scale.

Exploratory analyses to assess orthogonal measures of plasma kallikrein enzyme activity (peptide reporter substrate assay) will be performed. Descriptive statistics will be presented for the rate of activity and % inhibition result. A test comparing the % inhibition change and change from baseline to zero within each group will be calculated and a within group p-value will be presented at each visit and timepoint.

The mean and median % inhibition versus time profiles will be plotted by cohort on a linear scale. Individual values versus time plots by treatment and spaghetti plots with subject levels versus time profiles by cohort will also be provided on a linear scale.

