9.7. Pharmacodynamic Analysis

Pharmacodynamic analyses will be conducted on data from participants in the PD Analysis Set. Descriptive statistics will be presented for plasma kallikrein activity levels and change and percentage change from baseline levels will be presented at each visit.

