### 5.2 Data Conventions

- **Period definition:**
  - **Screening/Run-In Period:** Starts at the Screening visit until the day before first treatment, approximately Study Day -56 to -1. If a participant has an HAE attack during the Run-In period before Day 1, all signs and symptoms of the HAE attack must be resolved before dosing.
  - **Treatment & Follow-up Period:** The period from date of first dose to End of Study Date.
  - **End of Study Date:** The latest of date of Early Termination visit or as designated by “End of Study” CRF page.
  - **Treatment Period (for HAE assessments)** is defined in [Section 9.1](#); for this period the last scheduled visit for each cohort is Day 168 visit for cohort 1, Day 251 visit for cohort 2, and Day 195 visit for cohort 3. The last assessment date or last dose date can be used for participants that have not reached the end of their cohort’s treatment period.
  - **First Dose Period (for HAE assessments)** is defined as the first dose until participant’s second dose (cohorts 2 & 3) or end of treatment period.
  - **Study day:** Relative to the date of first treatment of STAR-0215: assessment date – first treatment date (+1 if assessment is after first treatment).
- **Conversion factors:**
  - 1 month = 30.4375 days
  - 1 year = 365.25 days
  - 1 week = 7 days
- **Additional rules**
  - (Absolute) Change from baseline = Value at the time point – Baseline value.
  - Relative change from baseline = [(Value at the time point – Baseline value) / Baseline value] x 100.

- % inhibition (of pharmacodynamic assessments) =  $1 - [\text{postdose rate} / \text{predose rate}] \times 100$ .
- Duration on Study = (End of Study Date – Date of First STAR-0215 treatment) +1.
- Duration of Treatment Period = (Last Treatment period assessment date – Date of First STAR-0215 treatment) +1.

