### 6.2 General Statistical Methods

#### 6.2.1 General Methods

All outputs will be incorporated into Microsoft Excel or Word files, sorted and labeled according to the International Conference on Harmonization (ICH) recommendations, and formatted to the appropriate page size(s).

Tabulations will be produced for appropriate demographic, baseline, efficacy, PK, PD, Immunogenicity and safety parameters. For categorical variables, summary tabulations of the number and percentage within each category (with a category for missing data) of the parameter will be presented. For continuous variables, the mean, median, standard deviation, Q1, Q3, minimum and maximum values will be presented. The PK summaries will additionally include the percent coefficient of variation (CV%), geometric mean, and geometric CV%. Descriptive statistics for categorical variables will consist of frequency counts and percentages.

Results will be presented by cohort.

No formal statistical hypothesis testing will be performed. Summary statistics will be presented, as well as 95% confidence intervals (CI) on selected parameters, as described in the sections below.

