### 6.2.4 Multiple Comparisons/Multiplicity

No adjustments for multiplicity will be made.

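### SAP 5.2 misplaces a bracket in % inhibition, and SAP 6.5.2 asks for unadjusted p-values from an unnamed test although SAP 6.2.1 rules out formal testing

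*SAP*

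**What the plan says.** **Derivation rule.** SAP 5.2 gives % inhibition for PD assessments as "1 - [\text{postdose rate} / \text{predose rate}] \times 100" (typesetting codes left in). The only bracket is around the ratio. In the same list the relative-change rule is fully bracketed: "Relative change from baseline = [(Value at the time point – Baseline value) / Baseline value] x 100".

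**Use of the rule.** SAP 6.5.2 applies % inhibition to the peptide reporter substrate assay, which it introduces as exploratory. It asks for descriptive statistics, plots of the mean and median over time, and a test against zero. The secondary PD measure, %cHMWK, uses absolute and percentage change instead.

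**P-values.** For %cHMWK, SAP 6.5.2 says "A test comparing the percent change and absolute change from baseline within each group will be calculated" and that "a within group p-value will be presented at each visit and timepoint". A parallel sentence covers the peptide assay, for the change in % inhibition and the change from baseline. Neither sentence names the test, and the first gives no reference value.

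**Rest of the plan.** SAP 6.2.1: "No formal statistical hypothesis testing will be performed"; it offers summary statistics, with 95% confidence intervals on selected parameters. SAP 6.2.4: "No adjustments for multiplicity will be made". Protocol 9.7: "Descriptive statistics will be presented for plasma kallikrein activity levels", with change and percentage change by visit and no mention of a test. SAP Section 7 reports no departures from the protocol's analyses other than the revised Section 2.5 text.

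**The concern.** A derivation rule in a SAP is what the programmer implements and the validator checks against. If the printed rule is wrong, either the outputs are wrong or someone departs from the SAP without a record.

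The p-values are a separate matter. A plan that disclaims formal testing, and gives the attack-rate endpoint only a confidence interval, nevertheless produces a grid of unadjusted p-values in cohorts of 4 to 12 people. With no test named, they cannot be reproduced from the SAP. With no label, a reader of the study report cannot tell whether they are descriptive or evidential. SAP 2.5 says the interim outputs follow Section 6, and that the analysis of the first 16 participants is run alongside one of all dosed participants. The grid would therefore be produced more than once.

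**Working it through.** The documents give no number of PD tests and no significance level, so there is no plan figure to reproduce.

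**A. The formula**

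Inputs: the rule in SAP 5.2; baseline as the last value before the first dose (SAP 6.2.2). Let r = postdose rate / predose rate, taking predose as that baseline.

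- As printed: I(r) = 1 - 100r
- As evidently intended: J(r) = 100(1 - r) = 100 - 100r
- Difference: I(r) - J(r) = 1 - 100 = -99 for every r

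| r | As printed | Intended |
|---|---|---|
| 1 (no inhibition) | -99 | 0 |
| 0.5 | -49 | 50 |
| 0.1 | -9 | 90 |
| 0.01 | 0 | 99 |
| 0 (full inhibition) | +1 | 100 |

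Because the error is a constant shift:

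- Means, medians, quartiles, extremes and plotted levels are all 99 points too low. Standard deviations are unaffected.
- Change from baseline is correct. Baseline has r = 1, so the change is (1 - 100r) - (1 - 100) = 100(1 - r).
- A test of the level against zero is wrong. A participant with no inhibition sits at -99, and one with 99% inhibition sits at 0.

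The %cHMWK results use the relative-change rule and are not touched.

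**B. The number of p-values**

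Post-baseline PD samples in the schedules of assessments (Protocol 1.1, SAP 9.1):

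- Cohort 1: 4 h; Days 2, 7, 14, 28, 56, 84, 112, 140, 168 = 10
- Cohort 2: 4 h; Days 2, 7, 14, 28, 56, 84 pre, 84 post, 85, 90, 97, 111, 139, 167, 209, 251 = 16
- Cohort 3: 4 h; Days 2, 7, 14, 28 pre, 28 post, 29, 34, 41, 55, 83, 111, 153, 195 = 14
- Total: 10 + 16 + 14 = 40

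SAP 6.5.2 names two quantities for each of two assays. The count depends on the reading:

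| Reading | P-values |
|---|---|
| Two tests per assay, both assays at all 40 timepoints | 40 x 4 = 160 |
| Same, without the five 4-hour samples | 35 x 4 = 140 |
| Peptide assay on the serum/plasma sampling row only (5 + 10 + 8 = 23 timepoints) | 40 x 2 + 23 x 2 = 126 |
| One of the two sentences read as a single test | 40 x 3 = 120 |
| Both sentences read as single tests | 40 x 2 = 80 |

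The third reading is possible because Protocol 7.13.4.1 lists alternative measures of plasma kallikrein activity among the serum/plasma biomarkers, and Protocol 7.13.4 says not every assay need be run at every timepoint. The row label is partly blacked out, so this cannot be settled. Combining that reading with single tests would give 40 + 23 = 63.

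**C. The sections side by side**

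| Source | Position on PD p-values |
|---|---|
| SAP 6.5.2 | Required throughout, test unnamed |
| SAP 6.2.1 | No formal testing; summaries and 95% CIs |
| SAP 6.2.4 | No adjustment |
| Protocol 9.7 | Descriptive statistics |
| SAP Section 7 | No such change declared |

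**The case against.** The formula is plainly a slip. The quantity is labelled % inhibition, the neighbouring rule is correctly bracketed, and -99 for an untreated sample would be noticed at once. It serves only an exploratory assay. All of that stands and limits the harm; it does not make the printed rule right.

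On the p-values, SAP 6.2.1 excludes only formal testing, and the absence of multiplicity adjustment fits nominal p-values. Protocol 9.2 leaves methodological detail to the SAP, and 9.11 leaves pre-planned exploratory analyses to it. Protocol 9.7 does not say that PD analysis is descriptive only. This also stands in part: the peptide-assay tests can be defended as exploratory, which leaves the %cHMWK p-values as the undeclared addition. But SAP 6.5.2 never calls its p-values nominal and never names the test.

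Three stronger inferences are tempting and are not supported:

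- *The test rejects when the drug does nothing.* SAP 6.5.2 speaks of the change in % inhibition. If that means change from baseline, the offset cancels and the test is sound. The harm arises only if the level is meant.
- *There are 160 tests, so 8 false positives are expected (160 x 0.05).* The count of 160 assumes the peptide assay at all 40 timepoints. The 8 also needs every test to attain 0.05, an assumed level. Under an exact signed-rank test (also an assumption) the smallest two-sided p is 2/2^4 = 0.125 for n = 4, so Cohort 1's 10 x 4 = 40 tests contribute none. The other (16 + 14) x 4 = 120 contribute at most 120 x 0.03125 = 3.75 for n = 6. No effect anywhere is in any case a weak benchmark for a kallikrein inhibitor measured on its own target.
- *The whole PD analysis is compromised.* %cHMWK does not use the faulty rule.

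**Conclusion.** Both defects are real and modest. The % inhibition rule is wrong as printed by a constant 99 points. Coded literally, that spoils the reported and plotted levels for the peptide assay, but not changes from baseline and not %cHMWK. Whether the test against zero is affected depends on whether it is applied to the level or to the change, and SAP 6.5.2 leaves this unclear.

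The p-value requirement does not fit SAP 6.2.1 or Protocol 9.7, and for %cHMWK it is missing from SAP Section 7. The size is roughly 80 to 160 p-values per full analysis; the mismatch holds at any count. Severity is moderate to minor: the primary endpoints are safety, the stopping rules rest on adverse events, and although PD results may inform adding participants, no stated rule uses these p-values.

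The conclusion assumes ordinary operator precedence and that predose means before the first dose.

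**What to change.** 1. In SAP 5.2 write: % inhibition = [1 - (postdose rate / predose rate)] x 100. This returns 0 for no inhibition and 100 for full inhibition.
2. In SAP 6.5.2 replace the two p-value sentences with mean change and mean % inhibition by cohort and timepoint, each with a 95% confidence interval. SAP 6.2.1 already allows this.
3. If any p-values are kept, name the test, state whether it applies to the level or to the change from baseline, label the results nominal and exploratory, and bring SAP 6.2.1 and Section 7 into line.

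The cost is SAP wording and the matching table shells. No data, visits or participants are added, and dropping the p-values loses nothing in a study that states no hypotheses.

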### 6.5.3 Immunogenicity (ADA) Evaluations

Analysis of ADA data will be based on the Safety Analysis Set.

The ADA status will be defined using the baseline and post-baseline results. Anti-drug antibody negative is defined as negative results at all time points. Anti-drug antibody positive is defined as a positive result at any time point, including baseline.

The number and percentage of participants with negative and positive ADA results will be tabulated by cohort.

The number and percentage of participants with ADA negative, positive, and missing results will be tabulated at baseline for the safety analysis set. Additionally, the number of participants with baseline and postbaseline samples will be presented.

Participants with negative baseline result with a positive ADA result post dose are considered treatment induced ADA status; Participants that are ADA positive at Baseline with a post-baseline ADA positive titer result  $\geq 4 \times$  Baseline value have treatment boosted ADA status. Treatment-emergent ADA participants have either treatment induced or treatment boosted ADA status.

Data will be summarized for ADA results at all time points. The incidence (defined as treatment induced plus treatment boosted) and prevalence (ADA positive at any time point) will be presented. Treatment induced is defined as negative at baseline and positive at any time point postbaseline. Treatment boosted is defined as positive at baseline and a postbaseline titer of at least 4 times the baseline positive titer result. Descriptive statistics will be presented for the positive titer values.

The incidence and prevalence will be summarized by cohort.

All ADA results will be presented in a data listing, by date for unscheduled or repeated values.

### 6.5.4 Biomarker Evaluations

The actual value and change from Baseline to each post-baseline evaluation will be summarized. Analysis will be based on the Safety Analysis Set.

## 6.6 Safety Evaluations

Safety analyses will be conducted using the Safety Analysis Set.

### 6.6.1 Adverse Events

Adverse events will be coded using MedDRA and will be graded using the severity scale specified in the protocol. .

Summaries of AEs will be based on treatment emergent AEs (TEAEs), defined as AEs with an onset at the time of or following the start of treatment, or medical conditions present before the start of treatment that increase in severity or relationship at the time of or following the start of treatment.

Adverse events are summarized by participant, therefore, in any tabulation, a participant contributes only once to the count for a given adverse event (SOC or PT).

Separate tabulations may also be produced for TEAEs assessed as related to study drug (related, probable, or possible relationship), TEAEs that led to discontinuation from study, TEAEs that led to death, TEAEs greater than or equal to Grade 3 in severity and TEAEs by highest grade. Common AEs will be summarized by MedDRA PT from most to least common. Treatment emergent SAEs and treatment emergent SAEs related to study drug will also be tabulated.

No formal hypothesis-testing analysis of adverse events incidence rates will be performed.

All adverse events occurring on study will be listed in subject data listings.

By-subject listings also will be provided for the following: participant deaths; serious adverse events; and adverse events leading to study discontinuation.

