9.4. Safety Analysis

9.4.1. Adverse Events Analysis

Adverse events will be coded using the Medical Dictionary for Regulatory Activities (MedDRA) Version 25.0 or higher and will be graded as described in Section 8.4.

Summaries of AEs will be based on treatment emergent AEs (TEAEs), defined as AEs with an onset at the time of or following the start of treatment with study drug, or medical conditions present before the start of treatment that increase in severity or relationship at the time of or following the start of treatment.

Treatment emergent AEs will be summarized separately for each dose level and by the number of participants experiencing TEAEs corresponding to MedDRA System Organ Classes (SOCs) and Preferred Terms (PTs) by highest grade.

Separate tabulations may also be produced for TEAEs assessed as related to study drug, TEAEs that led to treatment discontinuation, TEAEs that led to death, and TEAEs greater than or equal to Grade 3 in severity. Common AEs will be summarized by MedDRA PT from most to least common. Treatment emergent SAEs and treatment emergent SAEs related to study drug will also be tabulated.

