## 1.2 Objectives

**Table 1: STAR-0215 Objectives & Endpoints**

Primary Objective	Primary Endpoints

 
To assess the safety and tolerability of SC administration of single and multiple doses of STAR-0215 in participants with Type I or Type II HAE
 
	
 
Incidence of adverse events
 
Changes in vital signs, ECG findings, physical examination findings, and clinical laboratory evaluations
 

Secondary Objectives	Secondary Endpoints

 
To assess the clinical activity of SC administration of single and multiple doses of STAR-0215 in participants with Type I or Type II HAE
 
To characterize the PK of SC administration of single and multiple doses of STAR-0215 in participants with Type I or Type II HAE
 
	
 
Change from baseline in monthly HAE attack rate
 
Incidence of HAE attack severity (mild, moderate, and severe)
 
Duration of HAE attack (shorter than 12 hours, 12 to 24 hours, 24 to 48 hours, and longer than 48 hours)
 
The number of HAE attacks requiring on-demand- therapy
 
Time to first HAE attack after first and last dosing
 
Concentration of STAR-0215 and the derived PK parameters
 

 
• To characterize the PD of SC administration of single and multiple doses of STAR-0215 in participants with Type I or Type II HAE
 
• To assess the immunogenicity of SC administration of single and multiple doses of STAR-0215 in participants with Type I or Type II HAE
 
	
 
• Change in plasma kallikrein activity
 
• Formation of anti-drug (STAR-0215) antibodies
 

Exploratory Objectives	Exploratory Endpoints

 
• To evaluate the impact of STAR-0215 on [REDACTED] of STAR-0215
 
• To conduct an exploratory assessment of the effect of STAR-0215 on [REDACTED] in participants with Type I or Type II HAE
 
	
 
• Changes from baseline in [REDACTED] STAR-0215
 
• Changes from baseline in the [REDACTED]
 

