Provided no safety concerns are noted from a cumulative review of safety data from this study and the ongoing FIH study (STAR-0215-101), [REDACTED] and [REDACTED] may be explored in [REDACTED]

STAR-0215 will be administered SC into the abdomen. There are planned to be 4 participants in Cohort 1, 6 participants in Cohort 2, and 6 participants in Cohort 3. Based on the accumulated safety information and enrollment as continually monitored by the SRC [REDACTED] (Protocol Section 9.12), up to 6 additional participants may be added to Cohort 2 and/or Cohort 3 (maximum of 12 participants each in Cohorts 2 and 3) [REDACTED]

████████████████████ The dose regimens and dose levels for each cohort are in Table 2. There is no placebo group in this study. An overview of the study design is provided in Table 3.

[figure not shown]
As detailed in the [Schedules of Assessments](#), study assessments will be performed in all cohorts through 6 months after the last dose of STAR-0215 (Day 168 in Cohort 1, Day 251 in Cohort 2, and Day 195 in Cohort 3). At this time, participants who are willing and eligible to consent can begin participation in the long-term open label extension study (STAR-0215-202). For participants who do not enroll in the long-term open label extension study, safety monitoring will be performed through ██████ months after the last dose of STAR-0215 in all cohorts (Day ██████ in Cohort 1, Day ██████ in Cohort 2, and Day ██████ in Cohort 3) through regular contacts and scheduled site visit. Visits subsequent to STAR-0215 administration are scheduled with respect to the actual day of STAR-0215 dosing for consistency and precision in post-dose sample collection. Safety assessments (including AEs, vital signs, ECGs, physical examinations, clinical laboratory evaluations, and pregnancy testing), and efficacy, PK, PD, immunogenicity, biomarker, and ████████████████████ may be conducted at scheduled site visits.

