## 7 CHANGES TO [REDACTED]

Protocol text related to Section 2.5 [REDACTED] was revised: due to fast enrollment each [REDACTED] will include additional participants and available [REDACTED] data.

Otherwise, there have been no changes between the protocol-defined statistical analyses and those presented in this statistical plan.

A [REDACTED] will take place when the first 16 participants dosed have completed treatment follow-up. Separate analyses will be performed for the “initial 16 participants’ and for all cumulative data at the time of the data cut-off.

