5 The hematology assessment will be a CBC with differential.

6 The chemistry assessment includes total protein, albumin, glucose, alkaline phosphatase, bilirubin (total and direct), aspartate aminotransferase, alanine aminotransferase, gamma-glutamyl transferase, lactate dehydrogenase, uric acid, blood urea nitrogen, creatinine, calcium, sodium, potassium, chloride, carbon dioxide, phosphate, magnesium, cholesterol, triglycerides, and creatine phosphokinase.

7 The coagulation assessment includes international normalized ratio, activated partial thromboplastin time, and prothrombin time.

8 The urinalysis includes pH, glucose, ketones, blood, specific gravity, nitrite, protein, bilirubin, and microscopy (if urinalysis is abnormal).

- 9 Vital signs (including blood pressure, heart rate, respiratory rate, and body temperature) will be taken prior to blood sample collection and after the participant has been in a supine position for at least 5 minutes. Vital signs will be taken pre-dose within 4 hours of dosing and 4 hours ( $\pm 30$  minutes) post-dose.
- 10 Height collected at Screening only. Complete physical examinations will be performed at Screening and the post-dose timepoint on Day 1. All other physical examinations will be a targeted evaluation of general appearance, skin, abdomen, and cardiovascular and respiratory systems. The Day 1 post-dose physical examination will be performed at 4 hours ( $\pm 30$  minutes).
- 11 During the Run-In period, the weekly contacts will be conducted on Days ( $\pm 1$ ) -49, -42, -35, -28, -21, -14, and -7. HAE attacks will be collected from the time of informed consent.
- 12 On Day 1, PK and PD blood samples will be collected pre-dose and 4 hours  $\pm 15$  minutes post-dose.
- 13 Blood sample collection for pharmacogenetics/-omics testing is optional and requires additional participant consent.
- 14 All AEs will be recorded from the time of informed consent through the final study visit.
- 15 For participants who do enroll in the long-term open label extension study, this will serve as the final visit with end of study assessments.
- 16 Remote visits to collect concomitant medication and AE assessments including information regarding pregnancy and HAE attacks.
- 17 On-site visit to collect concomitant medication and AE assessments including information regarding pregnancy and HAE attacks.

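### The TEAE tables mix both doses and unequal follow-up within each cohort, so cohort percentages are not directly comparable and single-dose 600 mg safety can be read only from listings

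*SAP*

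**What the plan says.** The primary objective (SAP Table 1) is "To assess the safety and tolerability of SC administration of single and multiple doses of STAR-0215" in participants with Type I or II HAE, and AE incidence is the first primary endpoint listed (SAP 3.1). The counting rule in SAP 6.6.1 is: "Adverse events are summarized by participant, therefore, in any tabulation, a participant contributes only once to the count for a given adverse event", at SOC or PT level. An event is treatment-emergent if it starts or worsens at or after the start of treatment. No end date is given. The unit of presentation comes from SAP 6.2.1: "Results will be presented by cohort".

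Cohort 1 receives one dose. Cohorts 2 and 3 receive a second dose on Day 84 and Day 28 (SAP Table 2). Study assessments run to about six months after the last dose: "Day 168 in Cohort 1, Day 251 in Cohort 2, and Day 195 in Cohort 3" (SAP 2.1). AE collection can run longer: "All AEs will be recorded from the time of informed consent through the final study visit" (note to the Cohort 1 schedule; the other two schedules say the same). Participants who do not enter STAR-0215-202 are monitored for further months, the number of which is redacted. Under protocol 8.2.1, their HAE attacks in that later phase are reported as AEs. Before it, attacks are not AEs unless serious.

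SAP 5.2 defines a First Dose Period that ends at the second dose, but only for HAE assessments. SAP 6.4.1 and 6.4.2 use it for attack rate and attack-free proportion. SAP 6.5.1 gives PK parameters by dose. The AE section has nothing equivalent.

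**The concern.** A proportion of participants with at least one event depends on how long they are watched and how often they are dosed. Here both differ between columns, and the planned table shows neither.

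Three things follow:

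- A longer-watched cohort is expected to show a higher percentage even if the drug behaves identically in all cohorts.
- In Cohorts 2 and 3 a participant with the same event after each dose is counted once, so the tables show neither recurrence nor a change after Dose 2.
- Cohorts 2 and 3 have identical exposure, one 600 mg dose, until Cohort 3 is dosed again at about Day 28. No table presents that shared experience, although the objective names single as well as multiple doses.

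The open-ended window adds a further problem. Protocol 2.4.1 expects that about six months after the last dose concentrations may no longer suppress attacks. Attacks from waning effect would then enter the TEAE table, but only for participants who did not roll over.

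**Working it through.** **1. The plan's own schedule.** Days after last dose at the six-month visit: 168 − 1 = 167, 251 − 84 = 167, 195 − 28 = 167. Follow-up after the last dose is equal by design. Time from the first dose, which is where TEAE counting starts, is not: 168, 251 and 195 days. At 30.4375 days per month (SAP 5.2) this is 5.52, 8.25 and 6.41 months. The ratios to Cohort 1 are 251/168 = 1.49 and 195/168 = 1.16.

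**2. Effect of unequal time.** The documents give no AE rate, so I assume a constant first-event rate λ per participant-month, the same in every cohort, over the range 0.01 to 0.5. Expected crude incidence is 1 − exp(−λ × T / 30.4375), with T in days.

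| λ per month | Cohort 1 | Cohort 2 | Cohort 3 | Cohort 2 − 1 (points) |
|---|---|---|---|---|
| 0.01 | 5.4% | 7.9% | 6.2% | 2.5 |
| 0.02 | 10.5% | 15.2% | 12.0% | 4.8 |
| 0.05 | 24.1% | 33.8% | 27.4% | 9.7 |
| 0.10 | 42.4% | 56.2% | 47.3% | 13.7 |
| 0.15 | 56.3% | 71.0% | 61.7% | 14.7 |
| 0.20 | 66.8% | 80.8% | 72.2% | 13.9 |
| 0.50 | 93.7% | 98.4% | 95.9% | 4.7 |

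Differences are taken before rounding. The maximum is 14.7 points, near λ = 0.15. In participants this is 6 × 0.147 = 0.88 at n=6 and 12 × 0.147 = 1.76 at n=12. Cohort 3 exceeds Cohort 1 by 0.8 to 5.4 points.

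**3. Against chance.** At λ = 0.10, with 4 participants in Cohort 1 and 6 in Cohort 2, the standard error of the difference is √(0.424 × 0.576/4 + 0.562 × 0.438/6) = 0.32, or 32 points. With 12 in Cohort 2 it is 29 points. From exact binomials (4 v 6), the Cohort 2 proportion exceeds Cohort 1 with probability 0.61, against 0.45 if both were followed for 168 days. It falls below Cohort 1 with probability 0.28.

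**4. Follow-up beyond six months.** Its length is redacted, so I vary it at λ = 0.10. If everyone is followed 3, 6 or 12 months longer, the Cohort 2 − 1 gap falls from 13.7 to 10.2, 7.5 or 4.1 points. If roll-over differs by cohort, the gap can reverse. With 6 extra months for all of Cohort 1 and none for Cohort 2, the values are 68.4% and 56.2%.

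**5. Events that cluster after dosing.** If each dose carries probability 0.20 independently and time adds nothing, a one-dose cohort shows 20% and a two-dose cohort 1 − 0.80² = 36%. A table by dosing period would show 20% after each dose.

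**6. What a common window does.** With the equal-rate assumption and λ = 0.10, the first 28 days give 8.8% in all three cohorts, and the 167 days after last dose give 42.2% in all three. Events per participant-month are 0.10 throughout.

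**7. Information on a single 600 mg dose.** Combined, Cohorts 2 and 3 give n = 12 to 24, against 6 to 12 per cohort. With no events, the one-sided 95% upper bound 1 − 0.05^(1/n) is 39% at n=6, 22% at n=12 and 12% at n=24.

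**The case against.** The case for leaving the plan alone has real weight. This is a non-randomized, descriptive study of at most 28 participants, with no hypothesis tests and no planned between-cohort safety comparison. Cohort 1 is a pure single-dose column. All AEs are listed by participant, onset date and time are collected (protocol 8.5), and dosing is listed by cohort, so a careful reader can place each event relative to Dose 2. Laboratory values, vital signs and ECGs are summarized over scheduled visits on both sides of Dose 2. All of this stands, and it limits the point to the AE tables. It does not remove it: Cohort 1 is 4 participants at 450 mg and says nothing about a single 600 mg dose, and listings are a weak summary of the first-listed primary endpoint.

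Three stronger readings are tempting but not supported.

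- *The tables make single-dose and multiple-dose safety inseparable.* They do not, given Cohort 1 and the listings. What is missing is a tabulated single-dose summary at 600 mg and a before-and-after view within Cohorts 2 and 3.
- *Cohort 2 will look worse.* The expected excess is small beside chance, rests on a constant rate, and can shrink or reverse with follow-up after six months.
- *The SAP silently departed from the protocol.* Protocol 9.4.1 says "Treatment emergent AEs will be summarized separately for each dose level and by the number of participants experiencing TEAEs", and SAP section 7 says "Otherwise, there have been no changes between the protocol-defined statistical analyses and those presented in this statistical plan". However, protocol 9.2 itself presents results by cohort, protocol 9.3 analyzes by assigned dose cohort, and protocol 9.4.2 to 9.4.5 use dose and dose cohort interchangeably. This is loose wording. It should be tidied, because dose level is ambiguous for Cohort 2 (600 then 300 mg), but it is not an undeclared change.

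**Conclusion.** The point holds as a limitation of the AE tables. By-cohort TEAE percentages are not directly comparable, and in Cohorts 2 and 3 they combine events before and after the second dose. The missing split and the missing cut-off can be read from the text and need no assumption.

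The size of the follow-up effect does rest on assumptions: a constant, equal event rate and follow-up ending at the six-month visit. On those terms the expected Cohort 2 excess over Cohort 1 is 2.5 to 14.7 points across the range examined, which is under one participant at n=6 and under two at n=12. The tables can suggest a cohort difference where there is none, and a reader should not infer more than that. The change is worth making because it gives a better summary of a primary endpoint at little cost.

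**What to change.** Keep the by-cohort tables. In SAP 5.2 and 6.6.1:

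- Extend the First Dose Period to TEAEs, and tabulate TEAEs for (a) Dose 1 to the actual Dose 2 date, or to the six-month visit in Cohort 1; (b) Dose 2 to the six-month visit; and (c) after the six-month visit, shown separately, with HAE attacks reported as AEs identified. Use the actual date because Dose 2 has a window (±2 days at Day 28, ±3 at Day 84).
- Give participants at risk and events per participant-month for each period.
- Add one table from Dose 1 to the earlier of Day 28 or the actual Dose 2, with Cohorts 2 and 3 combined (600 mg) beside Cohort 1 (450 mg). SAP 5.3 plans no pooling, so state this exception there.
- Describe the periods as time since dosing. Dose 1 exposure persists after Dose 2, so the second period does not isolate the second dose.
- Align the dose-level wording in protocol 9.4.1 with the SAP's cohort.

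The cost is SAP text, a few more tables from dates already collected, and one wording alignment. No procedure or data collection changes. The downside is small counts per cell.
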